4.4 Sample size estimate

Sample size is based on the known prevalence of SCD in Nigeria (SCD prevalence of 2.39% and a carrier rate of about 23%)¹⁹, using the following formula and a 95% confidence interval.¹⁷

1. Specify clinically acceptable values for the width of 95% confidence interval (CI), sensitivity (SN), specificity (SP), and the disease prevalence (P).
2. Calculate the number of patients with disease, defined as the sum of true positive cases (TP) and false negative cases (FN) using:

$$TP + FN = Z_{\alpha/2}^2 \frac{SN(1 - SN)}{W^2}$$

3. Calculate the sample size required to obtain the desired sensitivity as:

$$N1 = \frac{TP + FN}{P}$$

4. Calculate the number of patients without disease, defined as the sum of true negative cases (TN) and false positive cases (FP) using:

$$TN + FP = Z_{\alpha/2}^2 \frac{SP(1 - SP)}{W^2}$$

5. Calculate the sample size required to obtain the desired specificity as:

$$N2 = \frac{TN + FP}{P}$$

Where $Z_{\alpha/2}$ is a statistical constant having a value of 1.96 for 95% CI.

6. Select the required sample size as the greater of N1 and N2.

The calculations made for the HemeChip test sample size are summarized in Table 1 below:

Prevalence estimate	P	0.024
Width of the 95% CI: 10%	W	0.10
Sensitivity expected: 98%	SN	0.97
Specificity expected: 98%	SP	0.97
Statistical constant, 1.96 for 95% CI	Zalpha	1.96
Number with disease, True Positive + False Negative	TP+FN	11
Sample size required for sensitivity	N1	468
Number without disease, False Positive + True Negative	FP+TN	11
Sample size required for specificity	N2	11
FINAL SAMPLE SIZE (greater of N1 and N2)		468

Total maximum enrollment of 5,000 patients, age 6 weeks to 60 months identified through CAPIBD.

Procedure

The CAPIBD medical officer will introduce the study and ask if parent/caregiver is willing to participate. If yes, signed informed consent will be obtained and the subject assigned a unique identification number through CAPIBD. The clinical research assistant (CRA) assigned to the study will complete a questionnaire including demographic data and family information, and perform a heel or finger prick to obtain a blood sample for HemeChip and HPLC (page 12).

HemeChip Test

- a. Finger-stick or heel-stick blood sample (20 μ L) is mixed with deionized water for red blood cell lysis and the mixture allowed to set for 3 minutes.
- b. 65 μ L of a buffer solution is used to wet the paper inside the HemeChip.
- c. A disposable metal applicator is used to stamp 1 μ L of the mixture onto the paper strip inside the HemeChip through the sample application port.
- d. 185 μ L of the buffer solution is pipetted into two buffer chambers through buffer loading inlets on the HemeChip.
- e. The HemeChip is loaded into the reader and the power supply in the reader turned on. The test runs for five minutes and diagnosis is obtained on a computer connected to the reader.
- f. Data is stored on computer and results delivered by fax delivery and secured email to a dedicated port for the attention of study PI.
- g. Study CRA contacts caregivers of screen-positive children via phone and all who screen positive will be referred to the local SCD clinic for follow up care.

HPLC Test

- a. All blood samples collected via heel or finger prick on dot-blot paper will be shipped to the IFAIN lab in Abuja on a monthly basis.

- b. HPLC confirmatory results will be obtained from the IFAIN lab on a monthly basis.
- c. Study CRA contacts caregivers of screen-positive babies via phone following confirmatory results.
- d. All subjects with abnormal HPLC results will be enrolled in the pediatric sickle cell clinic, for parental education, penicillin prophylaxis, pneumococcal vaccination, malaria prevention, fever and pain management protocol, splenic palpation and contact with SCD team.

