2. AIMS

2.1 General objective

The primary study objective is to validate the HemeChip technology as a novel, point-of care (POC) platform for screening SCD. The results obtained using the HemeChip will be compared to High Performance Liquid Chromatography (HPLC), and the sensitivity and specificity of the HemeChip will be determined.

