4.5 Statistical analysis

Data will be analyzed and reported based on established methods in the literature.¹⁸ Statistical significance will be set at 95% confidence level for all tests ($p < 0.05$). Receiver-operating curves will be utilized to assess sensitivity and specificity of

HemeChip in comparison to HPLC as the standard test. Sensitivity will be calculated as $\# \text{ true positives} / (\# \text{ true positives} + \# \text{ false negatives})$ and specificity will be calculated as $\# \text{ true negatives} / (\# \text{ true negatives} + \# \text{ false positives})$. Positive predictive value (PPV) will be calculated as $\# \text{ true positives} / (\# \text{ true positives} + \# \text{ false positives})$ and negative predictive value (NPV) will be calculated as $\# \text{ true negatives} / (\# \text{ true negatives} + \# \text{ false negatives})$.

5 Dissemination of results

Study results will be disseminated at a clinical meeting in the Department of Child Health at Case Western Reserve University, published in peer-reviewed scientific journals and presented at relevant scientific conferences.

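### Table 1 promises a 10% width for the 95% CI but enters 0.10 as a half-width, so 468 children (about 11 SCD cases) cannot give that precision for sensitivity

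*Combined protocol and SAP*

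**What the plan says.** The general objective (section 2.1) is that "the sensitivity and specificity of the HemeChip will be determined" against HPLC, so sensitivity is one of two primary measures.

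Section 4.4 sizes the study by the precision of those two measures. Step 1 asks for a clinically acceptable width of the 95% interval. Table 1 then gives "Width of the 95% CI: 10" per cent, with W = 0.10. Step 2 computes the number of diseased children as Z²·SN(1 − SN)/W², and step 3 divides by prevalence. The table reports 11 diseased children, N1 = 468, and 468 on the line "FINAL SAMPLE SIZE (greater of N1 and N2").

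Directly below the table comes "Total maximum enrollment of 5,000 patients, age 6 weeks to 60 months identified through CAPIBD". No precision is given for that number, and the text does not say how it relates to 468.

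Section 4.5 defines sensitivity, specificity, PPV and NPV as point estimates. For method it says only "Data will be analyzed and reported based on established methods in the literature"; it names no confidence interval.

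**The concern.** The width of an interval is the distance between its two limits. The printed formula comes from setting Z·√(SN(1 − SN)/n) equal to W, and that quantity is the distance from the estimate to one limit. The label and the formula therefore differ by a factor of 2 in width, and of 4 in the number of cases. Nothing in section 4.4 says half-width or plus/minus.

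The formula also relies on a normal approximation for a proportion close to 1 with 11 observations, where it is not usable.

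The precision of sensitivity depends only on the number of SCD cases. If enrolment stopped near 468, readers would have been told to expect a 10-point interval and would get one two to three times as wide on average. Even a perfect observed result could not exclude a true sensitivity in the low 70s (Clopper-Pearson). For a screening test, the uncertainty lies in how many affected children it misses.

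**Working it through.** **Inputs (section 4.4).** Z = 1.96; W = 0.10; SN = 0.97 in the value column (its label says 98%); prevalence 2.39% in the text, rounded to 0.024 in Table 1.

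**Reproducing the plan's figure.**

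- Cases: 1.96² × 0.97 × 0.03 / 0.10² = 11.18.
- Children: 11.18 / 0.0239 = 467.7, rounded up to 468. (With 0.024 the result is 465.8.)
- With SN = 0.98 the formula gives 7.53 cases and 315 children, so the table used 0.97.

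The plan's 11 and 468 appear only when 0.10 is the half-width.

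**What 468 gives on the plan's own formula.** At 11.18 cases, 1.96 × √(0.97 × 0.03 / 11.18) = 0.100, so the total width is 0.20. For a total width of 0.10, W must be 0.05: 1.96² × 0.97 × 0.03 / 0.05² = 44.72 cases, and 44.72 / 0.0239 = 1,871 children.

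**Whether the formula can be trusted at 11 cases.**

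- Expected misses: 11 × 0.03 = 0.33.
- Probability that none is missed: 0.97¹¹ = 72%. The Wald interval then has zero width.
- Actual coverage of the nominal 95% Wald interval, summed over Binomial(11, 0.97): 28%.

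**Small-sample intervals at 11 cases.** Clopper-Pearson and Jeffreys limits are beta quantiles; Wilson is in closed form. Expected widths are averages over the binomial distribution.

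| Interval | 11 of 11 detected | Expected width, SN 0.97 | Expected width, SN 0.98 |
|---|---|---|---|
| Jeffreys | 80.0% to 100% | 24.4 points | 23.0 points |
| Wilson | 74.1% to 100% | 29.1 points | 28.1 points |
| Clopper-Pearson | 71.5% to 100% | 32.4 points | 31.2 points |

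With one miss (10 of 11) the Clopper-Pearson interval is 58.7% to 99.8%.

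**Variation in the number of cases.** Under Binomial(468, 0.0239) the 95% range is 5 to 18 cases, and the chance of 8 or fewer is 21%. With 8 of 8 detected, Clopper-Pearson gives 63.1% to 100%.

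**Numbers needed for an expected total width of 10 points (SN 0.97, prevalence 2.39%).**

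| Interval | Cases | Children |
|---|---|---|
| Jeffreys | 47 | about 1,967 |
| Wilson | 58 | about 2,427 |
| Clopper-Pearson | 64 | about 2,678 |

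**At the enrolment maximum.** 5,000 × 0.0239 = 119.5, about 120 cases; the expected Clopper-Pearson width is 6.9 points.

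**Specificity at 468.** 468 − 11 = 457 non-cases; the expected Clopper-Pearson width at 0.97 is 3.3 points, well inside the target.

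**The case against.** The strongest reply is the 5,000 maximum. No section says that enrolment stops at 468. One can read 468 as the formula's minimum and 5,000 as the ceiling, and any total above about 1,900 to 2,700 would meet the 10-point target. On that reading the fault is a wrong label and an unexplained gap, not a shown shortfall. This limits the consequence but does not remove the error. A maximum is not a target, the table calls 468 final, and a study that stopped there would comply with the document and miss its stated precision.

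Second, section 4.5 does not commit to Wald intervals, so their zero width and 28% coverage describe an analysis that the plan does not specify. That is fair. Those figures show only that the planning formula is unreliable here; the width error stands without them.

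Third, the multiple depends on the interval: 2.0 on the plan's formula, 2.4 to 3.2 on the others. True, but every one is at least double.

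Fourth, 2.39% is a national figure, and the cohort is acutely ill children at three hospitals. The documents give no prevalence for them. At an assumed 5%, 468 children give 468 × 0.05 = 23 cases, still short of 45.

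Fifth, relabelling W as a half-width presumes what the sponsor meant. The relabel describes what the formula does. If a 10-point total width was intended, it is the sample size that must change.

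**Conclusion.** The concern holds. By the plan's own formula, 468 children give a total width of about 20 points for sensitivity, not 10, and a 10-point width needs about four times as many (1,871). With intervals suited to 11 cases, the expected width is 24 to 32 points.

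Reading W as plus/minus 10 does not rescue the figure: with 11 of 11 detected, the Clopper-Pearson lower limit lies 28.5 points below the estimate, and with 10 of 11 it lies 90.9 − 58.7 = 32.2 points below.

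The result assumes the plan's prevalence of 2.39% and a true sensitivity of 0.97; at 0.98 the conclusion is the same. It applies to sensitivity at 468 children. It does not apply to specificity, nor to a study that enrols close to 5,000. It must be fixed because the only stated final sample size rests on it.

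**What to change.** 1. In step 1 and Table 1, label W as the half-width of the 95% CI, 10 percentage points. Beside it, state what 468 delivers, for example: *About 11 SCD cases are expected (95% range 5 to 18 at a prevalence of 2.39%). The Clopper-Pearson 95% CI for sensitivity is 71.5% to 100% if all 11 are detected and 58.7% to 99.8% with one miss.* Make the 98% labels agree with the 0.97 values while the table is open.
2. Say whether 468 or a larger number is the enrolment target, and how it relates to 5,000. If enrolment is to go further, give the precision at that number. Expected Clopper-Pearson widths are 12.3 points at 1,871 children (45 cases), 9.9 at 2,678 (64 cases) and 6.9 at 5,000 (120 cases).
3. In section 4.5, state that sensitivity, specificity, PPV and NPV will be reported with Wilson or Clopper-Pearson 95% intervals. This supports the first two changes; either method will do.

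All three are changes of wording and add no patients. The cost is a less favourable stated precision. If a true 10-point total width is wanted and 468 was the real target, the cost is considerable: 2,678 / 468 = 5.7 times as many HemeChip and HPLC tests, though still within the 5,000 maximum.

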3. LITERATURE REVIEW

Despite its recognition as a global public health problem, SCD remains a neglected health priority in many low- and middle-income countries. Ironically, the burden of haemoglobinopathies is projected to increase in the coming decades. By 2050, it is estimated that the proportion of sickle cell anaemia births in sub-Saharan Africa will be about 88% of the worldwide total, compared to 79% in 2010. This increase will be largely as a result of population growth and public health transition.⁵

The pathophysiology of SCD includes premature red cell haemolysis, vascular obstruction, endothelial damage, chronic inflammation and infarction. These result in acute and chronic complications such as severe anaemia, bone pain, stroke and end organ damage.^{6,7} Complications may begin during infancy particularly in individuals with homozygous disease. Newborn screening for SCD has been shown to be highly effective in reducing the morbidity and mortality associated with SCD, when linked to comprehensive healthcare services.^{8,9} National programs for routine, universal newborn screening for SCD are lacking in many African countries, Nigeria inclusive.¹⁰ Consequently, most children are diagnosed opportunistically, when they present to health facilities with clinical symptoms and signs suggestive of SCD.

Standard diagnostic testing for sickle cell disease include cellulose acetate or citrate agar electrophoresis (bench top electrophoresis), IEF, high performance liquid chromatography (HPLC), capillary electrophoresis and molecular analysis.¹¹

Bench top Hb electrophoresis: This is a laboratory method that can be done under alkaline or acidic conditions and with a variety of sieving materials such as gel or paper.¹² Under alkaline conditions, Hb types C, A2, S, F, and A have net negative charges and migrate towards the positively charged electrode forming visible bands that can be used to identify various Hb disorders. Although useful for the rapid screening of a small number of samples, its results may suffer from inaccuracies at low concentrations. Moreover, alkaline Hb electrophoresis has the disadvantage of having poor resolution between HbS and HbF, particularly in neonates who have high HbF levels, which may result in inaccurate identification of overlapping bands.

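### Sample size (4.4): the 468 children that justify the plan yield about 11 SCD cases, which cannot give sensitivity the stated 10-point precision; the exact 95% CI is 71.5% to 100% even if no case is missed

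*Combined protocol and SAP*

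**What the plan says.** The comparison of HemeChip with HPLC, giving sensitivity and specificity, is the primary objective (2.1). Section 4.4 opens with "Sample size is based on the known prevalence of SCD in Nigeria", put at 2.39% in the text and 0.024 in Table 1.

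The table has a row "Width of the 95% CI: 10" (per cent), with W = 0.10, and a row "Sensitivity expected: 98" (per cent), whose value column holds 0.97. The row "Number with disease, True Positive + False Negative" then gives 11, N1 is 468 and N2 is 11. The row beginning "FINAL SAMPLE SIZE (greater of N1 and N2" gives 468.

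Directly below the table stands "Total maximum enrollment of 5,000 patients, age 6 weeks to 60 months identified through CAPIBD". Nothing connects that figure to 468.

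In 4.5 the definition beginning "Sensitivity will be calculated as" gives the usual ratio of true positives to all diseased. The section sets a 95% confidence level for tests and points to a reference for methods, but it names no confidence interval for sensitivity or specificity.

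**The concern.** Interval precision is the only reason given for 468, and sensitivity alone determines that number. The formula assumes that the estimated proportion is roughly normal. With 11 cases and a true sensitivity of 0.97, the most likely result is no false negative at all, and the formula's own interval then has zero width.

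For a screening test, sensitivity measures how many affected children are missed. The stated precision implies a lower limit near 87% (0.97 − 0.10) if W is a half-width, or near 92% (0.97 − 0.05) if it is a full width. If the data cannot support such a limit, a report of 100% sensitivity from 468 children would look far firmer than it is.

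**Working it through.** **Inputs (4.4 and Table 1).** P = 0.0239 (text) or 0.024 (table); W = 0.10; SN = 0.97 in the value column, 98% in the label; Z = 1.96.

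**1. Reproduce the plan.**
- Cases = Z² × SN(1 − SN) / W² = 1.96² × 0.97 × 0.03 / 0.10² = 11.18, printed as 11.
- N1 = 11.18 / 0.0239 = 467.7, so 468 (with 0.024 it is 465.8).
- The table therefore uses 0.97. With the label's 98%, 1.96² × 0.98 × 0.02 / 0.01 = 7.53, or 8 cases, and 7.53 / 0.024 = 313.7, or 314 children.
- The formula uses W as a half-width. Reading the label literally (total width 0.10, half-width 0.05), the same formula would give 44.7 cases.

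**2. Does the approximation apply?** Expected false negatives are 11 × 0.03 = 0.33. The chance of 11/11 is 0.97¹¹ = 71.5%, and of 10/11 it is 24.3%. At 11/11 the normal-approximation interval collapses to 100% to 100%. Its true coverage at n = 11 and sensitivity 0.97 is 28%, not 95%.

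**3. Valid intervals with 11 cases.** When all n cases are detected, the exact (Clopper-Pearson) lower limit is 0.025^(1/n).

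| Result | Exact 95% CI | Wilson 95% CI |
|---|---|---|
| 11/11 | 71.5% to 100% | 74.1% to 100% |
| 10/11 | 58.7% to 99.8% | 62.3% to 98.4% |

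Averaged over the binomial distribution at 0.97, the exact width is 32.4 points (Wilson 29.1), and the lower limit lies 29.6 points below the estimate (Wilson 26.7). The targets are 20 and 10 points respectively for W as a half-width, and a total width of 10 points for W as a full width. With the label's 98% and 8 cases, 8/8 gives 63.1% to 100%.

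**4. The case count is itself random.** For Binomial(468, 0.0239) the mean is 11.2 and the 95% range is 5 to 18. Full detection gives a lower limit of 47.8% at 5/5 and 81.5% at 18/18.

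**5. Cases needed at sensitivity 0.97** (exact intervals; N = cases / 0.024).

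| Criterion, on average | Cases | N, about | Wilson cases |
|---|---|---|---|
| Total width ≤ 20 points | 22 | 917 | 20 |
| Lower limit within 10 points of the estimate | 44 | 1,833 | 43 |
| Total width ≤ 10 points | 64 | 2,667 | 58 |

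At 5,000 children, 5,000 × 0.024 = 120 cases, and 116/120 gives 91.7% to 99.1%.

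**6. If prevalence is higher.** The documents give no figure for the enrolled children, so these values are assumptions, at N = 468.
- 5%: about 23 cases, lower limit 85.2% if all are detected. The mean width is 19 points, but the mean lower limit is still 17 points below the estimate.
- 9%: about 42 cases, lower limit 91.6% if all are detected.

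**7. Specificity.** 468 − 11 = 457 children without SCD; 443/457 (96.9%) gives an exact 94.9% to 98.3%. There is no problem here.

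**The case against.** Four points can be made for the plan.

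- **The 5,000 maximum.** At P = 0.0239 it would yield 99 to 141 cases (95% range), enough for every criterion above. This is true, but it is stated as a maximum. A study that stopped at 468 would comply with the document and miss its own precision. The objection limits the finding to enrolment near 468 and does not remove it.
- **Prevalence.** Enrolled children are acutely ill in hospital, and the literature review says "most children are diagnosed opportunistically, when they present to health facilities with clinical symptoms and signs suggestive of SCD". That points towards more cases than the national figure predicts. An SCD prevalence of about 4.7% (22/468) would bring the mean exact width within 20 points. The possibility is real, but the plan neither states nor relies on it.
- **Choice of benchmark.** Section 4.4 speaks of interval width. On the mildest reading (20 points in total) the shortfall is twofold, 22 cases against 11. It becomes fourfold only if the lower limit must lie within 10 points of the estimate. The full-width reading comes from the label, not from the formula. All this is fair, and all three thresholds are shown for that reason; 11 cases meet none of them.
- **Interval method.** Section 4.5 defers to a reference, and the choice is often made at analysis. However, a default normal-approximation interval at 11/11 would show no uncertainty at all, so leaving it open matters here.

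**Conclusion.** The concern holds: the precision claimed for 468 is wrong as written for sensitivity. At the plan's prevalence, 468 children give about 11 cases, and even with every case detected a sensitivity of 72% could not be excluded. The mean interval is about 30 points wide, against 20 or 10 intended. The conclusion is the same for exact and Wilson intervals and for both readings of W.

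It rests on P of about 2.4%, a true sensitivity near 0.97, and enrolment ending near 468. A clearly higher hospital prevalence, or recruitment well beyond 468, would reduce or remove the shortfall; the plan commits to neither. Because this precision is the sole justification for the sample size and bears on half of the primary objective, it must be fixed.

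**What to change.** 1. **In 4.4**, replace the 10-point precision at 468 with the exact figure for about 11 cases (lower limit 71.5% even if all are detected). Say that it depends on P of about 2.4%, state whether W is a half-width or a full width, and make the sensitivity and specificity labels (98%) agree with their values (0.97).
2. **In 4.5**, name Wilson or Clopper-Pearson 95% intervals for sensitivity and specificity.
3. **State how 468 relates to the 5,000 maximum** and where recruitment ends. Print exact precision against the number of HPLC-confirmed SCD cases, for example 11, 22, 44, 64 and 120.

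These changes cost some wording, one short table and a standard interval function. They add no patients, though the precision quoted for 468 becomes less favourable.

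Whether to recruit beyond 468 is the sponsor's decision and not part of the required change. As a rough upper bound, the literature review's ceiling of $50 per HPLC test gives (1,833 − 468) × $50 = $68,250 to reach 44 expected cases, or (5,000 − 468) × $50 = $226,600 to reach the maximum, for HPLC alone. The study's own unit cost is not given and may be lower.

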4.4 Data handling and quality assurance

The PI will ensure the accuracy, completeness, and timeliness of the data recorded. Only the investigators and designated study personnel will have access to these data. Identified patients will be given a unique study number through CAPIBD and only the study number will be included in the dataset. Once a complete dataset has been gathered on all patients, the identifiers will be discarded, and only the de-identified data will be maintained. Study personnel will enter data from source documents corresponding to a subject's visit into the protocol-specific electronic Case Report Form (eCRF). All data collected during the course of this study will be reviewed and verified for completeness and accuracy by the PI.

The data will be entered into a validated database, which will allow safe and secure storage. After data have been entered into the study database, a system of computerized data validation checks will be implemented and applied to the database on a regular basis. Any changes to the study database will be documented.

